6.4.1. Preparation and Dispensing

See the IPM for instructions on how to prepare the study intervention for administration. Study intervention should be prepared and dispensed by an appropriately medically qualified and experienced member of the study staff (eg, physician, nurse, physician's assistant, nurse practitioner, pharmacy assistant/technician, or pharmacist) as allowed by local, state, and institutional guidance. A second staff member will verify the preparation and dispensing.

6.5. Measures to Minimize Bias: Randomization and Blinding

6.5.1. Randomization to Study Intervention

Randomization of participants to vaccine groups will proceed through the use of an IRT system. The site personnel (study coordinator or specified designee) will be required to enter or select information including but not limited to the user's ID and password, the protocol number, and the participant number. The site personnel will then be provided with a vaccine assignment, randomization number, and DU or container number when study intervention is being supplied via the IRT system. The IRT system will provide a confirmation report containing the participant number, randomization number, and DU or container number assigned. The confirmation report must be stored in the site's files.

The study-specific IRT reference manual and IPM will provide the contact information and further details on the use of the IRT system.

6.5.2. Blinding Arrangements

This study is double-blinded.

6.5.2.1. Blinding of Study Site Personnel

The participant, study coordinator, and all site staff will be blinded.

Please refer to the IPM for further details.

6.5.2.2. Blinding of the Sponsor

The majority of sponsor staff will be blinded to study intervention allocation. All laboratory testing personnel performing serological assays or diagnostic assays will remain blinded to the study intervention assigned/received throughout the study.

6.5.3. Breaking the Blind

The IRT will be programmed with blind-breaking instructions. In case of an emergency, the investigator has the sole responsibility for determining if unblinding of a participant's vaccine assignment is warranted. Participant safety must always be the first consideration in making such a determination. If the investigator decides that unblinding is warranted, the investigator should make every effort to contact the sponsor prior to unblinding a participant's vaccine assignment unless this could delay further management of the participant. If a participant's vaccine assignment is unblinded, the sponsor must be notified within 24 hours after breaking the blind. The date and reason that the blind was broken must be recorded in the source documentation and CRF.

The study-specific IRT reference manual and IPM will provide the contact information and further details on the use of the IRT system.

6.6. Study Intervention Compliance

Participants will receive study intervention directly from the investigator or designee, under medical supervision. The date and time of administration will be recorded in the source documents and in the CRF. The study intervention identification details and study participant identification will be checked and confirmed at the time of and prior to administration by a second member of the study site staff who is not the person administering the vaccine.

The site will complete the required vaccine Preparation Record located in the IPM. The use of the Preparation Record is preferred, but it does not preclude the use of an existing appropriate clinical site documentation system. The existing clinical site's documentation system should capture all pertinent/required information on the preparation and administration of the dose. This may be used in place of the Preparation Record after approval from the sponsor and/or designee.

6.7. Dose Modification

Not applicable.

6.8. Continued Access to Study Intervention After the End of the Study

No intervention will be provided to study participants at the end of their study participation.

6.9. Treatment of Overdose

For this study, any dose of study intervention greater than 1 dose of study intervention within a 24-hour time period will be considered an overdose.

There is no specific treatment for an overdose.

In the event of an overdose, the investigator should:

- Contact the medical monitor within 24 hours.
- Closely monitor the participant for any AEs/SAEs.
- Document the quantity of the excess dose as well as the duration of the overdose in the CRF.
- Overdose is reportable to Pfizer Safety **only when associated with an SAE**.

6.10. Concomitant Therapy

6.10.1. Prohibited Concomitant Vaccinations and Medications

- Licensed or nonstudy investigational RSV vaccines are prohibited at any time prior to enrollment and thereafter during the course of the study.
- Investigational vaccines and investigational drugs are prohibited within 28 days prior to enrollment and at any time during the study.

6.10.2. Withholding Periods for Concomitant Vaccinations and Medications

Unless considered medically necessary, the following restrictions apply to nonstudy licensed vaccines and medications as well as COVID-19 vaccines authorized for temporary or emergency use:

- Nonstudy nonlive vaccines (including licensed or authorized COVID-19 vaccines) may not be given within 14 days before or after study intervention administration.
- Nonstudy live vaccines should not be given within 28 days before or within 28 days after study intervention administration.
- Systemic corticosteroids (≥ 20 mg/day of prednisone or equivalent) for ≥ 14 days should not be given within 28 days before study intervention administration through the conclusion of study participation.

- Chronic systemic treatment with known immunosuppressant medications should not be given within 60 days before study intervention administration through the conclusion of study participation.
- Blood/plasma products or immunoglobulin should not be given within 60 days before study intervention administration through the conclusion of study participation.
- Prophylactic antipyretics and other pain medication to prevent symptoms associated with study intervention administration are not permitted.

6.10.3. Permitted Nonstudy Vaccines and Medications During the Study

The following restrictions apply to permitted vaccines and medications (except when they are considered medically necessary):

- Nonstudy nonlive vaccines (including licensed or authorized COVID-19 vaccines) may be given starting 14 days after the Visit 2 study intervention administration.
- Nonstudy live vaccines may only be given after study completion.
- Inhaled/nebulized, intra-articular, intrabursal, or topical (eg, skin, eyes) corticosteroids are permitted.
- Chronic corticosteroids that do not exceed a dose equivalent to 10 mg/day of prednisone are permitted for participants with COPD or asthma
- The use of antipyretics and other pain medication to treat symptoms associated with study intervention administration is permitted.
- Medication other than that listed in [Section 6.10.1](#) and [Section 6.10.2](#), required for treatment of preexisting stable conditions, is permitted.

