5.4. Screen Failures

Screen failures are defined as participants who consent to participate in the clinical study but are not subsequently randomly assigned to study intervention. A minimal set of screen failure information is required to ensure transparent reporting of screen failure participants to meet the CONSORT publishing requirements and to respond to queries from regulatory authorities. Minimal information includes demography, screen failure details, eligibility criteria, and any SAE.

Individuals who do not meet the criteria for participation in this study (screen failure) may be rescreened under a new participant number.

5.5. Criteria for Temporarily Delaying Enrollment/Randomization/Administration of Study Intervention

The following conditions may allow a participant to be vaccinated once the conditions have resolved and the participant is otherwise eligible:

- Current febrile illness (body temperature $\geq 38^{\circ}\text{C}$ [$\geq 100.4^{\circ}\text{F}$]) or other acute illness within 48 hours before study intervention administration.
- Receipt of any inactivated vaccine, licensed COVID-19 vaccines, or COVID-19 vaccines authorized for temporary or emergency use within 14 days or any live vaccine within 28 days before study intervention administration.
- Receipt of short-term (<14 days) systemic corticosteroids. Study intervention administration should be delayed until systemic corticosteroid use has been discontinued for at least 28 days. Inhaled/nebulized, intra-articular, intrabursal, or topical (skin or eyes) corticosteroids are permitted.

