9.1.2. Statistical Hypotheses

9.1.2.1. Statistical Hypothesis for Primary RSV Immunogenicity

The primary immunogenicity objective on immune response elicited by RSVpreF will be evaluated by the following hypothesis for both RSV A and RSV B as measured by NT:

$$H_{01}: \ln(\mu_1) - \ln(\mu_2) \leq \ln(0.667)$$

where $\ln(0.667)$ corresponds to a 1.5-fold margin for noninferiority and $\ln(\mu_1)$ and $\ln(\mu_2)$ are the natural log of the geometric mean of NT at 1 month after vaccination with RSVpreF for the coadministration group (Visit 2) and the sequential-administration group (Visit 3), respectively. Noninferiority will be declared if the lower limit of the 2-sided 95% CI for the GMR (coadministration group to sequential-administration group) is >0.667 for both RSV A and RSV B NTs.

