2.1.1. Primary Estimand(s)

2.1.1.1. Primary RSV Immunogenicity Estimands

The primary estimands for the RSV immunogenicity objective will use the hypothetical strategy and compare the RSVpreF immune response in participants without the intercurrent events. In other words, the immune response is estimated in the hypothetical setting where participants follow the study schedule and protocol requirements as directed. It includes the following 5 attributes:

- **Treatment condition:** RSVpreF administered at Visit 1 in the coadministration group vs RSVpreF administered at the Month 1 visit (Visit 2) in the sequential-administration group.
- **Population:** Older adults, as defined by the study inclusion and exclusion criteria.
- **Variables:** RSV serum NTs for subgroup A and subgroup B measured at the Month 1 visit in the coadministration group and RSV NTs for subgroup A and subgroup B measured at the Month 2 visit for the sequential-administration group.
- **Intercurrent events:** The following intercurrent events could impact the interpretation or the measurement of the immune response:
 1. The participant did not receive the study intervention as randomized.
 2. The participant did not meet the study inclusion criteria or did meet the exclusion criteria.
 3. Major protocol violations: The participant received a prohibited vaccine or treatment that may alter the immune response.
 4. Blood was taken outside an acceptable window for immunogenicity evaluation (<25 days after RSVpreF administration or >49 days after RSVpreF administration).

The clinical question of interest is based on whether the immune response elicited from RSVpreF via coadministration with SIIV, without any influence from any other immune-modifying drugs or vaccines and measured at a homogeneous time window, is noninferior to that of RSVpreF administered alone (ie, without SIIV). Therefore, all data after intercurrent events 1, 2, and 3, as well as all data at intercurrent event 4, if collected, will be excluded. Major protocol violations will be determined by clinical review (through the data handling memo).

- **Population-level summary:** GMR, defined as the ratio of RSV A and RSV B neutralizing GMTs between the 2 treatment groups.

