4. ANALYSIS SETS (POPULATIONS FOR ANALYSIS)

Data for all participants will be assessed to determine if participants meet the criteria for inclusion in each analysis population prior to unblinding and releasing the database, and classifications will be documented per standard operating procedures.

Participant Analysis Set	Description
Enrolled	All participants who have a signed ICD.
Randomized population	All enrolled participants who are assigned a randomization number in the IRT system.
Safety population	All enrolled participants who receive the study intervention (RSVpreF, placebo, or SIIV).

Major protocol violations will be determined by clinical review. A major protocol violation is a protocol violation that, in the opinion of the sponsor’s study medical monitor, would materially affect assessment of immunogenicity or efficacy, eg, participant receipt of a prohibited vaccine or medication/treatment that might affect immune response or a medication error with suspected decrease in potency of the vaccine. The sponsor’s medical monitor will identify those participants with protocol violations before any analysis is carried out.

Defined Analysis Set	Description
Evaluable RSV immunogenicity population	All participants who meet the following criteria: 
 • Are eligible for the study; • Received the study interventions (RSVpreF, placebo, or SIIV) to which they were randomized at both Visit 1 and Visit 2; • Had the 1-month RSVpreF postvaccination blood collection 25 to 49 days after RSVpreF vaccination (25 days \leq Visit 2 - Visit 1 \leq 49 days for the coadministration group and 25 days \leq Visit 3 - Visit 2 \leq 49 days for the sequential-administration group); • Had no major protocol violations from randomization through the 1-month RSVpreF postvaccination blood draw; • Had at least 1 valid and determinate assay result (NT for RSV A or RSV B) 1 month after RSVpreF vaccination.

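### Permitted nonstudy vaccines can precede the primary RSV draw mainly in the sequential group, and no planned analysis isolates those titers

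*Protocol*

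**What the plan says.** **Timing of the draw.** Protocol 9.1.2.1 compares the 1-month RSV titers "for the coadministration group (Visit 2) and the sequential-administration group (Visit 3), respectively". Visit 2 is a dosing visit, and its sample is taken before the injection (Protocol 8.9.2). Visit 3 follows 28 to 35 days later and involves no dose.

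**Vaccine rules.** Under Protocol 6.10.2, nonstudy nonlive vaccines "may not be given within 14 days before or after study intervention administration". Protocol 5.5 lists "Receipt of any inactivated vaccine, licensed COVID-19 vaccines, or COVID-19 vaccines authorized for temporary or emergency use within 14 days" before dosing as a reason to delay it. Protocol 6.10.3 then gives the permission: "Nonstudy nonlive vaccines (including licensed or authorized COVID-19 vaccines) may be given starting 14 days after the Visit 2 study intervention administration". Sections 6.10.2 and 6.10.3 both make room for medical necessity; the wording in 6.10.3 is "except when they are considered medically necessary". Live vaccines wait until study completion under 6.10.3, so the point concerns nonlive vaccines.

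**Estimand and analysis set.** SAP 2.1.1.1 frames the RSV question as the response "without any influence from any other immune-modifying drugs or vaccines and measured at a homogeneous time window". Intercurrent event 3, which removes data, is limited to a prohibited vaccine or treatment. SAP 4 illustrates a major violation by "participant receipt of a prohibited vaccine or medication/treatment that might affect immune response".

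**What is recorded and reported.** All nonstudy vaccinations go on the CRF through the end of participation (Protocol 6.10.4). A summary by group is optional and may be replaced by a listing (SAP 6.5.3). The supplementary RSV analysis uses the mITT set under a treatment-policy strategy (SAP 6.1.1.2).

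**The concern.** The two arms are read at different visits, and the rule on other vaccines is tied to Visit 2 rather than to the time since RSVpreF. The same permission therefore opens after the primary draw in the coadministration group and before it in the sequential group. Randomization does not balance an exposure that arises from the visit at which each arm is read.

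The sequential group supplies the denominator of the GMR. If a vaccine given two or more weeks after RSVpreF lowered the 1-month RSV titer, the GMR would rise and noninferiority would be easier to declare. If it raised the titer, the GMR would fall and power would suffer. A permitted vaccine is not a prohibited one, so the stated exclusion rules do not reach it, although the estimand is worded to exclude outside influence.

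**Working it through.** **1. The plan's own figure.** Protocol 9.5 and Table 9 give 650 evaluable per group, an assumed true ratio of 0.9 (0.105 on the ln scale), a 1.5-fold margin, one-sided alpha 0.025, and SDs of 1.3 (RSV A) and 1.4 (RSV B).

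- SE for RSV A = 1.3 × √(2/650) = 0.0721.
- Power = Φ[(ln 1.5 − 0.105)/0.0721 − 1.96] = Φ(2.21) = 98.6%, as stated.
- RSV B gives 97.2% against 97.1% stated. The product of all six tests is 81.8% against 81.6% stated. The stated figure is the product of the rounded entries: 0.986⁴ × 0.971 × 0.889 = 0.816.

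The planning figures reproduce and serve as the scale below.

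**2. The open period between RSVpreF and the primary RSV draw.**

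| Group and rule | Protocol window (28–35 days) | SAP window (25–49 days) |
|---|---|---|
| Sequential, 6.10.3: day 14 to the Visit 3 draw | 28−14 to 35−14 = 14–21 days | 25−14 to 49−14 = 11–35 days |
| Coadministration, 6.10.3: permission starts after Visit 2 | 0 days | 0 days |
| Coadministration, 6.10.2 alone: Visit 1 + 14 to Visit 2 − 14 | 28−28 to 35−28 = 0–7 days | 0 to 49−28 = 0–21 days |

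The third row shows that 6.10.2 and 6.10.3 do not quite agree on the time between Visits 1 and 2. On either reading, the 14 days before the coadministration draw are closed, apart from medical necessity.

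**3. Whether any rule or analysis catches the exposed titers.** Intercurrent event 3 and the SAP 4 example both require a prohibited vaccine. The mITT analysis keeps the titers as well. The optional vaccine summary is not tied to the interval between RSVpreF and the draw. No planned analysis separates them.

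**4. Possible size.** The documents give neither the share p of the sequential group vaccinated before Visit 3 nor the factor f by which that vaccine changes the RSV titer. Both are assumed here, with no exposure in the coadministration group. The GMR is then multiplied by f^(−p). Error is the one-sided chance of passing RSV A when the true GMR is 0.667 (nominal 2.5%). Power is for RSV A at a true ratio of 0.9.

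| p | f | GMR multiplied by | Error, RSV A | Power, RSV A |
|---|---|---|---|---|
| 5% | 0.8 | 1.011 | 3.6% | 99.1% |
| 10% | 0.8 | 1.023 | 4.9% | 99.4% |
| 20% | 0.8 | 1.046 | 9.0% | 99.8% |
| 5% | 1.25 | 0.989 | 1.7% | 98.0% |
| 10% | 1.25 | 0.978 | 1.2% | 97.1% |
| 20% | 1.25 | 0.956 | 0.5% | 94.4% |

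With f = 1 there is no bias. For comparison, the 95% CI half-width for RSV A is 1.96 × 0.0721 = 0.141 on the ln scale, and the margin is ln 1.5 = 0.405. The error column is for one test; the overall claim requires all six.

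**The case against.** **Exposure is not strictly confined to one arm.** A reader might infer that only the sequential group can be exposed. The documents do not support that. The medical-necessity exception applies to both groups, and 6.10.2 alone leaves up to 7 days between Visits 1 and 2 unbarred on the protocol window. What stands is narrower: permitted vaccination in the final 14 days before the primary draw exists only in the sequential group.

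**The conflict with the estimand may be softer than it looks.** The adjective in SAP 2.1.1.1 may qualify vaccines as well as drugs. The sponsor may have judged that a nonlive vaccine given at least 14 days after RSVpreF does not alter the response. That is a fair reading, but neither document states or justifies it.

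**The effect may be negligible.** A reader might posit 20% uptake and a 30% titer loss, which gives 0.7^(−0.2) = 1.074, about half the CI half-width (ln 1.074 = 0.071 against 0.141). The documents do not support such a case. The protocol plans only a 10% loss for same-day coadministration, and Protocol 2.2.1 describes RSV responses given with SIIV as inconsistent rather than consistently lower. With f = 0.9 the factor is 1.011 at 10% uptake and 1.021 at 20%. On the ln scale the latter is 0.021, about 15% of the half-width and 5% of the margin. A vaccine given shortly before Visit 3 also has little time to act. This part of the objection largely stands.

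**Exclusion brings its own imbalance.** Dropping these titers removes participants almost only from the sequential arm, after randomization and on a self-selected behavior. That stands, and it is why exclusion from the main analysis should not be treated as the only acceptable remedy.

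**Most of the trial is untouched.** The four influenza comparisons are read at Visit 2 in both groups, so this mechanism does not affect them. Permitting late COVID-19 vaccination during a pandemic is a defensible design choice.

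**Conclusion.** The point holds as a gap between the vaccine rules and the stated RSV estimand. Titers drawn after a permitted vaccine stay in the evaluable RSV set, mainly in the comparator arm, and no planned analysis shows whether they matter. Only the two RSV tests are involved.

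The documents do not show that a bias exists, or which way it would run. The range of 0.96 to 1.05 for the GMR rests wholly on assumed uptake and effect, and the true figure is probably near 1. The discretion of the medical monitor does not close the gap, because a permitted vaccine is not a protocol violation. Judgment before unblinding is also poorly suited to it, since the same vaccine date after Visit 2 falls before the primary draw in one group and after it in the other. This is a cheap improvement rather than a threat to the trial's conclusion.

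**What to change.** 1. Reconcile Protocol 6.10.2, 6.10.3 and the SAP 2.1.1.1 estimand. The text should say whether nonlive vaccines are barred throughout the time between Visits 1 and 2, and whether a permitted vaccine counts as an influence that the estimand excludes. Which vaccine rule applies is for the sponsor to settle.
2. Tabulate by group any nonstudy vaccine received between RSVpreF and that group's primary RSV draw, including those given for medical necessity.
3. Prespecify, before unblinding, an RSV A and RSV B GMR analysis that leaves out titers drawn after such a vaccine. Use one programmed rule for both groups, and report it beside the analysis that keeps them.
4. If the sponsor holds to the estimand as worded, the same rule can become part of intercurrent event 3 for the main analysis, with matching text in SAP 4 and Protocol Table 5. The titers then stay in the mITT analysis.

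**Cost.** SAP wording, one derivation and one small extra analysis. Vaccinations are already recorded on the CRF; the derivation assumes that their dates are too. The exclusion will fall mostly on the sequential arm, so the report should give the number left out in each group and say that this analysis no longer compares the groups exactly as randomized.

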6.10.4. Recording Nonstudy Vaccinations and Concomitant Medications

The following concomitant medications and vaccinations will be recorded in the CRF:

- All nonstudy vaccinations including COVID-19 vaccines, received from 28 days prior to study enrollment through conclusion of study participation.
- Immunosuppressant medications, including monoclonal antibodies.
- Systemic corticosteroids, ie, oral, IM, or IV. Do not record topical, ophthalmic, otic, inhaled, intra-articular, or intrabursal corticosteroids.
- Blood/plasma products or immunoglobulin.

7. DISCONTINUATION OF STUDY INTERVENTION AND PARTICIPANT DISCONTINUATION/WITHDRAWAL

7.1. Discontinuation of Study Intervention

It may be necessary for a participant to permanently discontinue study intervention. Reasons for permanently discontinuation of study intervention include the following: AEs, participant request, investigator request, protocol deviation, no longer meeting all the inclusion criteria, or meeting 1 or more exclusion criteria.

Discontinuation of study intervention does not represent withdrawal from the study. If study intervention is discontinued, the participant will remain in the study to be evaluated for safety. Participants who remain in the study for evaluation of safety will be contacted by telephone 1 month after their last study vaccination to record AEs.

In the event of discontinuation of study intervention, it must be documented on the appropriate CRF/in the medical records whether the participant is discontinuing further receipt of study intervention or also from study procedures, posttreatment study follow-up, and/or future collection of additional information.

